14.9 Interim analyses

No interim analysis is planned for this study.

14.10 Expected Results

We expect to detect a significant protective effect of dupilumab on the postoperative control of sinonasal inflammation among participants with AFRS. This will be detected as a significant worsening of postoperative endoscopic mLK score and more frequent occurrences of needed rescue medications among the placebo group. We also anticipate a more conspicuous response to IL-4/13 blockade parallel with decreasing levels of Type 2 cytokines and eosinophil activation markers. While this study is not designed to detect a significant difference in secondary outcome measures, the collected data will nonetheless complement our exploratory studies seeking to define predictive biomarkers and mechanisms of treatment response.

Version: 3.7.3 2Apr2024

14.11 Safety evaluation plan

Safety outcomes will include the occurrence of any adverse events of special interest (AESI) as described in section 15.3.3. Cumulative incidence of AESIs will be used to evaluate safety. We will compare treatment groups using the risk difference and a 95% confidence interval for that difference at each of the five follow up time points in the study.

15. Provisions to Monitor the Data to Ensure the Safety of Participants

15.1 Obligations of Sponsor-Investigator

A sponsor-investigator assumes all sponsor responsibilities required by the FDA of the sponsor and the investigator, including those related to record keeping and prompt reporting of safety reports to the FDA. The responsibilities include:

- Selection of research staff qualified by training and experience
- Commitment to personally conduct or supervise the investigation according to the research plan
- Selection of study monitor(s) qualified to monitor the progress of the project
- Maintenance of accurate, complete, and current records, including correspondence with the FDA, monitor and IRB, records on shipment and disposition of drug and records of participants' case histories and exposure to the device
- Completion of regulatory filings, including amendments (supplemental applications)
- Timely submission of Final Report within 30 days of completion of investigation

15.2 Definitions

15.2.1 Adverse Event

An AE is any untoward medical occurrence in a subject administered a study drug which may or may not have a causal relationship with the study drug. Therefore, an AE is any unfavorable and unintended sign (including abnormal laboratory finding), symptom, or disease which is temporally associated with the use of a study drug, whether or not considered related to the study drug. An AE also includes any worsening (ie, any clinically significant change in frequency and/or intensity) of a pre-existing condition that is temporally associated with the use of the study drug. Routine laboratory monitoring is not a component of this study. If laboratory abnormalities are noted on laboratory testing obtained for other reasons or for work-up of an AE, these should be reported.

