AFRS

	1	
	BID	Twice a day
	CFR	Code of Federal Regulations
	CRSwNP	Chronic Rhinosinusitis with nasal polyps
	CT	Computed tomography
	EDC	Electronic Data Capture
	FU	Follow-up
	GCP	Good clinical practice
	ICF	Informed consent form
	IMP	Investigational medicinal product
	INCS	Intranasal corticosteroids
	IP	Investigational product
	IPD	IP discontinuation
	IRB	Institutional Review Board
	LMS	Lund-Mackay score
	mLK	Modified Lund Kennedy Endoscopic Score
	SNOT-22	SinoNasal Outcome Test, 22 item
	SoC	Standard of Care
	WOCBP	Women of childbearing potential
Funding	Sanofi	
Source		

Schema

2. Background

Allergic fungal rhinosinusitis (AFRS) is a severe form of eosinophilic nasal polyposis with critically inadequate treatment options for the 10% of chronic rhinosinusitis participants affected by the disease. Occlusive eosinophilic mucus and severe nasal polyposis presents in early adulthood, with an unrelenting course marked by sinus expansion and pressure-induced dehiscence of the surrounding orbit and skull base. Despite appropriate therapies with oral/topical corticosteroids, saline irrigations and comprehensive sinus surgery, nasal polyps aggressively recur, frequently within months of surgery. Medical options beyond topical and systemic steroids are limited. Neither antifungal nor allergen immunotherapy are beneficial. Due to persistent sinonasal inflammation, patients with AFRS receive an average of three corticosteroid bursts per year and revision sinus surgery every 42 months.

Rationale

In addition to the activation of type 2 inflammatory mediators found in other CRSwNP phenotypes, AFRS is uniquely characterized by an exaggerated activation of the adaptive immune response with serum IgE levels often above 1000 kU/L and defined by an upregulation of fungal specific IgE levels [1]. Marked eosinophilic inflammation is found throughout the upper airway, and the degree of mucosal eosinophil infiltration has been repeatedly reported as a potent predictor of poor surgical outcomes. We therefore hypothesize that dupilumab, a human monoclonal antibody that targets the type-2 inflammatory cascade, is a safe and effective treatment for nasal polyps as add-on therapy following endoscopic sinus surgery.

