3.3 Safety Objectives

Safety objective	Endpoint/variable(s)
Assess the safety of dupilumab after sinus	Continual reporting of events of special
surgery	interest (ESIs) and serious adverse events
	(SAEs)
	Physical examination

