14.7 Secondary and Exploratory analyses

In a secondary analysis, a similar mixed model as described above will be fit that includes the subset of participants who are receiving treatment (dupilumab or placebo) for both nostrils. This model will incorporate nesting factors to identify repeated measures by subject and by nostril.

In an exploratory analysis, we will also compare the proportion of participants whose modified Lund- Kennedy score improved by greater than or equal to 2 units. For participants who undergo sinus surgery for AFRS prior to Week 52, non-responder imputation will be used. We will utilize a Chi-square or Fisher's exact test to examine if this proportion is significantly different by treatment group (dupilumab or placebo) at 52 weeks.

For the continuous secondary outcomes (e.g. SNOT-22 score, NPS, FEV1), a mixed effects longitudinal model will be fit that includes group (dupilumab, placebo), time (randomization through post-treatment period), and their interaction term in a similar fashioned as described for the primary outcome modified Lund-Kennedy score. For the secondary outcomes that compare the number of participants requiring rescue treatment and the number of adverse events (safety) over 52 weeks, similar mixed effects models will be fit but with consideration of a Poisson distribution (as opposed to normal distribution). The mixed effects models for both primary and secondary outcomes will permit the inclusion of any significant potential confounders.

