15.3 Recording and Reporting Adverse Events

See Section 10.1- Discontinuation of study treatment for safety criteria resulting in study discontinuation.

Recording and reporting will be performed from the time the informed consent is signed until the EOS. The Participants or their legally authorized representative will report adverse events to the investigator or trained members of the study team.

The investigator is responsible for detecting, evaluating, recording, and evaluating all events that meet the definition of AEs and SAEs, by following the following steps:

- Review all documentation related to the event, including symptoms, clinic progress notes, laboratory reports, and diagnostic reports,
- Attempt to establish a diagnosis of the event and document as the AE /SAE
- Record the AE/SAE on the CRF
- Report to the sponsor

The investigator will also be reporting and following up with the events related to the study intervention or that caused the participant to discontinue the intervention.

The follow-up consists of further tests and examinations (laboratory, histopathological, consultation with other healthcare professionals) to demonstrate the nature and/or causality of the AE/SAE.

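### The between-arm AE count in section 14.7 takes in clinically significant worsening of AFRS itself, so it leans in dupilumab's favour if the drug works and can dilute a true excess of other AEs

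*Combined protocol and SAP*

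**What the plan says.** Section 15.2.1 counts an event as an AE whether or not it is related to study drug, and adds: "An AE also includes any worsening (ie, any clinically significant change in frequency and/or intensity) of a pre-existing condition". No visible section exempts AFRS, polyp recurrence or an acute exacerbation of CRS (AECRS). Section 15.3 makes recording complete: "The investigator is responsible for detecting, evaluating, recording, and evaluating all events that meet the definition of AEs and SAEs".

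Section 14.7 then plans a between-arm model for "the number of adverse events (safety) over 52 weeks, similar mixed effects models will be fit but with consideration of a Poisson distribution". The same sentence covers the number of participants needing rescue treatment. The AE count is not restricted by relatedness or type of event.

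Section 14.10 expects worse endoscopic scores and "more frequent occurrences of needed rescue medications among the placebo group".

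The other planned safety comparison is in section 14.11: "Cumulative incidence of AESIs will be used to evaluate safety", with a risk difference and 95% confidence interval at five time points. The AESI list in 15.3.3 contains no AFRS event. Section 3.3 names events of special interest, SAEs and physical examination as the safety endpoints; the total AE count is not among them.

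**The concern.** AFRS is a pre-existing condition for everyone randomized, and the protocol itself says which changes in it matter. Section 5.2.1 treats a rise of 2 or more mLK points from the postoperative baseline as clinically significant. Table 3 defines AECRS by symptoms of at least 7 days, a SNOT-22 rise above 9 and objective inflammation. On the wording of 15.2.1 such events qualify as AEs. They also feed the efficacy outcomes: mLK score, oral corticosteroid use, rescue medication and revision surgery.

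One exacerbation can therefore be counted once as efficacy and once as safety. If dupilumab reduces exacerbations, its AE count falls for a reason unrelated to tolerability.

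This matters because the clean analysis is narrow. Section 11 lists seven common reactions: injection site reactions, eosinophilia, insomnia, toothache, gastritis, arthralgia and conjunctivitis. The AESI list takes in only severe conjunctivitis and symptomatic eosinophilia. The other five, and the milder forms of those two, generally reach a planned between-arm model only through the 14.7 count.

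**Working it through.** **The plan's own figure.** The documents give no expected rate, effect or power for any AE comparison. The only design figure is 66 per arm for mLK (difference 2, SD 3.5, two-sided 0.05, 90% power). It reproduces: power at 66 per arm is 90.3% by the t-test. It enters below only as the arm size.

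**Inputs**
- *d*, AFRS-worsening AEs per participant-year on placebo. The nearest figure is in section 2 (Background): "patients with AFRS receive an average of three corticosteroid bursts per year". That describes AFRS patients in general, not a placebo arm just after surgery on INCS, so *d* is varied over 1, 2 and 3.
- *e*, the proportional reduction of those events on dupilumab: 0.3, 0.5, 0.6 (assumed).
- *b*, other AEs per participant-year on placebo: 2, 4 (assumed).
- *h*, the true rate ratio for other AEs: 1.50 (assumed).

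**Formula.** Placebo rate = d + b. Dupilumab rate = d(1 − e) + h·b. The 14.7 comparison estimates

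RR = [d(1 − e) + h·b] / (d + b).

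The harm is exactly cancelled when d·e = b(h − 1).

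**Worked cell.** With d = 3, e = 0.5, b = 2: placebo 3 + 2 = 5.0; dupilumab 1.5 + 3.0 = 4.5; RR = 4.5/5.0 = 0.90.

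**Full grid of RR, true ratio 1.50**

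| d | e | b = 2 | b = 4 |
|---|---|---|---|
| 1 | 0.3 | 1.23 | 1.34 |
| 1 | 0.5 | 1.17 | 1.30 |
| 1 | 0.6 | 1.13 | 1.28 |
| 2 | 0.3 | 1.10 | 1.23 |
| 2 | 0.5 | 1.00 | 1.17 |
| 2 | 0.6 | 0.95 | 1.13 |
| 3 | 0.3 | 1.02 | 1.16 |
| 3 | 0.5 | 0.90 | 1.07 |
| 3 | 0.6 | 0.84 | 1.03 |

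The range is 0.84 to 1.34. The ratio is below 1 in 3 cells, equal to 1 in 1 and diluted but above 1 in 14. The AFRS events removed from the dupilumab arm in a year number 66·d·e, from 66 × 1 × 0.3 ≈ 20 to 66 × 3 × 0.6 ≈ 119.

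**Precision in the worked cell** (Poisson, 66 per arm, one year). z = ln(RR) / √(1/events on placebo + 1/events on dupilumab).
- All AEs: 330 against 297 events, z = ln(0.90)/√(1/330 + 1/297) = −1.32.
- Other AEs only: 132 against 198 events, z = ln(1.50)/√(1/132 + 1/198) = +3.61.
- With the variance doubled for overdispersion: −0.93 and +2.55.

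**Wider range.** Taking b = 1, 2, 4; h = 1.25, 1.5; d = 0.5, 1, 3; e = 0.3, 0.5, 0.7 gives 54 combinations, each with a real harm. RR is below 1 in 20, exactly 1 in 3 and above 1 but diluted in 31. Eight of the 20 reversals pass z < −1.96 in the wrong direction; all eight are at d = 3. At d = 0.5, e = 0.5, b = 1, h = 1.5 the ratio is 1.17: diluted, not hidden.

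**The case against.** **The safety objective does not rest on this count.** A reader might infer that following the plan exactly would give the wrong answer on safety. The documents do not support that. Section 3.3 does not list the total AE count, and the AESI comparison in 14.11 is free of the overlap. The affected item is one clause among the secondary analyses, and 14.10 says the study is not designed to show differences in secondary outcomes. All of this stands. It limits the weight of the point, but the clause is still a planned comparison labelled as safety, and its bias is separate from low power.

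**Not every flare need be an AE.** Section 15.2.1 requires a clinically significant change in frequency or intensity. A participant flaring at the usual rate has arguably not changed, and how sites will code such events is an inference. This stands in part. It would be wrong to read every corticosteroid burst as an AE, or three a year as a forecast for the placebo arm, hence the lower values of *d*. The thresholds in section 5.2.1 and Table 3 still leave a class of AFRS events that fit the definition.

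**Reversal is not the usual result.** In 14 of the 18 cells the harm keeps its direction. That the ratio always falls below 1.50 is automatic once a reduced component is added, so it does not show severity.

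**The information to separate the events exists.** Investigators record a diagnosis (15.3) and a relatedness judgment (15.4.3), Appendix B lists the disease state as a reason for calling an event unrelated, and the DSMB may ask for safety data by arm in the format it chooses. This stands, but 14.7 uses none of it.

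**Excluding AFRS events has its own risk.** A drug-related sinonasal worsening would leave the count. This stands, and argues for showing both counts rather than replacing one with the other.

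**Conclusion.** The point holds in a limited form. Under the present wording the 14.7 count mixes the expected efficacy effect into a safety comparison. If dupilumab reduces AFRS worsening, the bias runs in its favour.

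Dilution of a true harm follows from the arithmetic. Cancellation or reversal depends on rates that the documents do not give, and it occurs in 4 of 18 cells of the main grid and 23 of 54 of the wider one. The conclusion also assumes that sites record AFRS worsening as AEs, as 15.2.1 and 15.3 read together require.

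The co-primary analyses and the AESI comparison are untouched. What is lost is a between-arm comparison, undistorted by efficacy, for the common reactions outside the AESI list. The gap should be closed before unblinding, since a split chosen afterwards could look selective.

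**What to change.** Leave the AE definition, reporting duties and clinical management unchanged. In 14.7, state that the between-arm comparison of the number of AEs will be reported twice, side by side: for all AEs, and excluding AFRS worsening (AECRS, nasal polyp recurrence, revision surgery for AFRS).

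Classify the excluded events from the recorded AE diagnosis together with the rescue and surgery records, by a rule written down and applied blind before unblinding. Table 3 alone will not do: it needs a SNOT-22 change and endoscopy or CT, while Table 1 schedules SNOT-22 and endoscopy only at visits 12 to 16 weeks apart during treatment. Exacerbations treated between visits might not be classifiable by it.

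The cost is a sentence or two in 14.7, a blinded review of AE terms and one more table. A drug-related sinonasal worsening might show only in the all-AE count, which is why that count stays beside the other.

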15.2.2 Serious Adverse Event

An SAE is any untoward medical occurrence that at any dose:

- Results in death includes all deaths, even those that appear to be completely unrelated to study drug (e.g., a car accident in which a subject is a passenger).
- Is life-threatening in the view of the investigator, the subject is at immediate risk of death at the time of the event. This does not include an AE that had it occurred in a more severe form, might have caused death.
- Requires in-patient hospitalization or prolongation of existing hospitalization. In-patient hospitalization is defined as admission to a hospital or an emergency room for longer than 24 hours. Prolongation of existing hospitalization is defined as a hospital stay that is longer than was originally anticipated for the event or is prolonged due to the development of a new AE as determined by the investigator or treating physician.
- Results in persistent or significant disability/incapacity (substantial disruption of one's ability to conduct normal life functions).

Version: 3.7.3 2Apr2024

• Is a congenital anomaly/birth defect

• Is an important medical event - Important medical events may not be immediately lifethreatening or result in death or hospitalization, but may jeopardize the subject or may require intervention to prevent one of the other serious outcomes listed above (e.g., intensive treatment in an emergency room or at home for allergic bronchospasm; blood dyscrasias or convulsions that do not result in hospitalization; or development of drug dependency or drug abuse).

15.3 Recording and Reporting Adverse Events

See Section 10.1- Discontinuation of study treatment for safety criteria resulting in study discontinuation.

Recording and reporting will be performed from the time the informed consent is signed until the EOS. The Participants or their legally authorized representative will report adverse events to the investigator or trained members of the study team.

The investigator is responsible for detecting, evaluating, recording, and evaluating all events that meet the definition of AEs and SAEs, by following the following steps:

- Review all documentation related to the event, including symptoms, clinic progress notes, laboratory reports, and diagnostic reports,
- Attempt to establish a diagnosis of the event and document as the AE /SAE
- Record the AE/SAE on the CRF
- Report to the sponsor

The investigator will also be reporting and following up with the events related to the study intervention or that caused the participant to discontinue the intervention.

The follow-up consists of further tests and examinations (laboratory, histopathological, consultation with other healthcare professionals) to demonstrate the nature and/or causality of the AE/SAE.

15.3.1 Adverse events

The site-Investigator (or designee) will transcribe the information in the CRF and enter in REDCap. The source documents will be kept with patients' records and be available for further review upon request.

15.3.2 Serious Adverse Events

All SAEs, regardless of assessment of causal relationship to study drug, must be reported to the Sponsor-Investigator within 24 hours. The S-I will be notified electronically through REDCap and/or email.

Information not available at the time of the initial report must be documented in a follow-up report. Substantiating data such as relevant hospital or medical records and diagnostic test reports may also be requested.

Version: 3.7.3 2Apr2024

15.3.3 Other Events that Require Accelerated Reporting

The following events are considered Adverse Event of Special Interest (AESI) and require reporting to the sponsor (or designee) within 24 hours of learning of the event:

- Anaphylactic reactions
- Systemic hypersensitivity reactions
- Helminthic infections
- Any severe type of conjunctivitis or blepharitis
- Keratitis
- Clinically symptomatic eosinophilia (or eosinophilia associated with clinical symptoms)
- Pregnancy of a female participant entered in a study as well as pregnancy occurring in a female partner of a male participant entered in the study with IMP;
 - Pregnancy occurring in a female participant entered in the clinical trial or in a female partner of a male participant entered in the clinical trial will be qualified as an SAE only if it fulfills one of the seriousness criteria.
 - In the event of pregnancy in a female participant, IMP should be discontinued.
 - Follow-up of the pregnancy in a female participant or in a female partner of a male participant is mandatory until the outcome has been determined.
 - Abnormal pregnancy outcomes (e.g., spontaneous abortion, fetal death, stillbirth, congenital anomalies, ectopic pregnancy) are considered SAEs.
- Significant ALT elevation
 - ALT >5 × ULN in participants with baseline ALT ≤2 × ULN; OR
 - ALT >8 × ULN if baseline ALT >2 × ULN.
- Symptomatic overdose (serious or nonserious) with IMP or other medication (NIMP)
 - An overdose (accidental or intentional) with the IMP is an event suspected by the Investigator or spontaneously notified by the participant and defined as at least twice the intended dose during an interval of less than 7 days. The circumstances (ie, accidental or intentional) should be clearly specified in the verbatim and symptoms, if any, entered on the AE forms.
 - An overdose (accidental or intentional) with any NIMP is an event suspected by the Investigator or spontaneously notified by the participant and defined as at least twice the maximum prescribed daily dose, within the intended therapeutic interval. The circumstances (ie, accidental or intentional) should be clearly specified.

Per FDA regulation 312.32, written IND safety reports will be submitted to the FDA by the IND sponsor, for serious, unexpected suspected adverse reactions within 15 calendar days of the sponsor determining that the event qualifies for reporting. If the event is fatal or is deemed to be life threatening, the report will be made within 7 calendar days of receipt of such information. The IND sponsor will also make an assessment of whether the event constitutes an unanticipated problem posing risks to participants or others (UP). This assessment will be provided to the Emory University IRB, which, in turn will make a final determination. If the Emory IRB determines an event is a UP it will notify the appropriate regulatory agencies and institutional officials.

15.4 Evaluation of Severity and Causality 15.4.1 Evaluation of Severity

The severity of AEs will be graded according to the Common Terminology Criteria for Adverse Events version 5.0 (CTCAE). Available:

https://ctep.cancer.gov/protocoldevelopment/electronic applications/docs/ctcae v5 quick refere nce 5x7.pdf

For adverse events not included in the standardized toxicity grading scale, the following scale will be used:

- Mild: Awareness of sign or symptom but is tolerated. Does not interfere in a significant manner with the subject's normal functioning level. It may be an annoyance. Prescription drugs are not ordinarily needed for relief of symptoms but may be given because of personality of the subject.
- Moderate: Discomfort that causes interference with normal activities. Produces some impairment of functioning but is not hazardous to health. It is uncomfortable or an embarrassment. Treatment for symptom may be needed.
- Severe: Incapacitating, with inability to perform normal activities. Produces significant impairment of functioning and is a definite hazard to the subject's health. Treatment for symptom may be given and/or subject hospitalized.

If a laboratory value is considered an AE, its severity should be based on the degree of physiological impairment the value indicates.

An event is "serious" if it meets one of the definitions described in section 15.2.2 (SAE), NOT when assessed as severe.

